#### 7.3.2.2. AEs by SOC and PT

The number of TEAEs and the number and percentage of patients with events will be presented by SOC and PT. Patients are counted once in each SOC and PT. Percentages will be based on the total number of treated patients in the treatment cohort. Treatment-emergent SAEs, treatmentemergent non-SAEs, and PTAEs will be summarized using the same approach.

#### 7.3.2.3. AEs by PT

The number of TEAEs and the number and percentage of patients with events will be presented by PT. Patients are counted once in each PT. Percentages will be based on the total number of treated patients in the treatment cohort.

#### 7.3.2.4. AEs and SAEs by SOC, PT, and Relationship

The number and percentage of patients with events will be presented by SOC and PT by grouped relationship (related, not related). If a patient has more than one occurrence of an AE, the strongest relationship to study treatment will be used in the summary table.

In addition, the number of AEs and the number and percentage of patients with AEs will be summarized by SOC and PT, and relationship result: not related, unlikely related, possibly related, probably related, or definitely related.

Lastly, the number of Related TEAEs and the number and percentage of patients with Related TEAEs will be summarized by SOC and PT, and separately by PT. The same analysis will be produced for Related treatment-emergent SAEs.

#### 7.3.2.5. AEs by SOC, PT, and Severity

The number and percentage of patients with events will be presented by SOC and PT by severity (mild, moderate, severe). If a patient has more than one occurrence of an AE, the most severe occurrence will be used in the summary table.

#### 7.3.2.6. Deaths

The AEs resulting in death will be presented in a listing.

#### 7.3.2.7. Adverse Events of Special Interest

#### 7.3.2.7.1. Hypersensitivity (IARs) and Injection Site Reactions (ISRs)

The number of Hypersensitivity (IARs) and number and percentage of patients with Hypersensitivity (IARs) will be presented by treatment cohort and overall by SOC and PT; the same analysis will be repeated separately for ISRs. Separate listings of Hypersensitivity (IARs) and ISRs will be produced.

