## 9.4.1.4. Recording Adverse Events

All observed or reported AEs regardless of treatment or causal relationship must be recorded and reported as described in Section 9.4.1.11.

For all AEs, the Investigator must obtain adequate information for the following:

- 1. Determine the outcome of the AE
- 2. Determine if the event meets criteria for an SAE
- 3. Assess the severity of the AE
- 4. Determine the causality of the AE

For all AEs, regardless of casual relationship, the Investigator must follow-up on the outcome of the event until the event or sequelae either resolve or stabilize.

Adverse events spontaneously reported by the patient, and/or parent or legal guardian and/or identified in response to an open-ended question from study personnel, or revealed by observation will be recorded during the study phase by the Investigator. Adverse event information will be collected from the signing of informed consent until completion of the study.

Adverse Events must be documented in clear, unambiguous medical terms. Study personnel are advised not to use abbreviations or acronyms.

For each AE record only the diagnosis on the AE page of eCRF, do not report the characteristic signs and symptoms of the diagnosis as additional AEs.

If a diagnosis is not available, record each sign and symptom as an AE, when a diagnosis becomes available, study personnel are to update the AE page of the eCRF with relevant diagnosis only.

Change in severity of an AE should be documented based on specific guidelines in the eCRF Completion Guidelines.

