## 9.4.2.1.1. Injection-Associated Reactions

Injection-associated reactions are defined as systemic signs or symptoms (eg, generalized urticaria or itching, hypotension, or respiratory distress) that occur within 3 hours after study drug administration that are assessed by the Investigator as possibly, probably, or definitely related to study drug.

Adverse events that are characterized as IARs may reflect a systemic hypersensitivity reaction (eg, combination of 2 or more of the following types of signs or symptoms: generalized urticaria or itching, hypotension, difficulty breathing, swelling of the eyelids or lips, or generalized edema). These AEs are to be captured as the individual AE(s) that occurred and are not to be grouped and recorded with the term "IAR" or "hypersensitivity."

For systemic hypersensitivity reactions, the investigational site will collect laboratory samples for analysis of the following:

- Tryptase (serum)
  - Within 1 hour from time of reaction onset, if possible (no longer than 2 hours after onset)
  - At 24 hours (or later) from time of reaction onset
- C5b-9 (EDTA plasma with protease inhibitors [P100 tubes])
  - Within 24 hours from time of reaction onset
- Hematology, blood chemistry, and urinalysis
  - Within 3 hours from time of reaction onset
  - At 24 hours from time of reaction onset

Patients will undergo a one-time pre-dose collection of serum for tryptase analysis on Day 1 prior to administration of study drug, in order to provide a Baseline tryptase value in case of a future IAR. The sample will be drawn only if the patient has no active allergies at the time, and will only be analyzed (along with the above assessments) if the patient experiences a subsequent acute or severe IAR. If the patient has an ongoing active allergic process on Day 1, the tryptase sample should be collected as soon as possible after the resolution of the allergic event.

Treatment guidelines can be found in the SOM.

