#### 5.3.1. Adverse Events (AEs)

Adverse events are defined in Protocol Section 9.4.1. This includes serious adverse events [SAEs], injection site reactions [ISRs], injection associated reactions [IARs], discontinuations due to AEs, drug-related serious and severe AEs. Also refer to Appendix 9.3 of this SAP for special handling of AEs.

Adverse events of special interest (AESI) include: ISR, Hypersensitivity (IAR), ectopic calcification, lipodystrophy, craniosynostosis, and chronic hepatitis. The AESI of ISR and hypersensitivity (IAR) will be identified by investigators as captured on case report forms. They will be supplemented by additional events identified by an Alexion clinical review and which are considered to be at least possibly related to study drug. The AESI of ectopic calcification, lipodystrophy, craniosynostosis, and chronic hepatitis will be identified by an Alexion clinical review irrespective of the event relationship to study drug.

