#### 7.3.2.1. Overall Summary of Adverse Events

An overall summary of the following categories of AEs will be presented by treatment cohort and overall, including summaries of events (n) and number of patients with events (n, %): TEAEs, treatment-emergent SAEs, and treatment-emergent non-SAEs. Within each category, the following subcategories will also be summarized:

- Mild/Moderate/Severe TEAEs
- Related TEAEs (possibly, probably, definitely related, or missing relationship)
- TEAEs leading to withdrawal from the study
- TEAEs leading to death
- AESI, see Section 7.3.2.7

A summary of events (n) and number of patients with events (n, %) for PTAEs will also be included with the following subcategories: Mild/Moderate/Severe AEs, AEs leading to withdrawal, and AEs leading to death (note that Related AEs and AESI do not apply to PTAEs).

A listing of all TEAEs by treatment cohort and patient will be presented. Separate listings will be produced for treatment-emergent SAEs, AEs leading to study drug withdrawal, AEs resulting in death, and PTAEs.

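### The planned number of injection-associated reactions (IARs) counts recorded signs, so a multi-sign reaction adds several events and no table gives the number of reactions per cohort

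*SAP*

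**What the plan says.** **Definition.** Protocol 9.4.2.1.1 defines IARs as "systemic signs or symptoms (eg, generalized urticaria or itching, hypotension, or respiratory distress) that occur within 3 hours after study drug administration" that the investigator judges possibly, probably or definitely related. It adds that such events may reflect a systemic hypersensitivity reaction, for example a "combination of 2 or more of the following types of signs or symptoms", and lists five types.

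**Recording.** The same section continues: "These AEs are to be captured as the individual AE(s) that occurred and are not to be grouped and recorded with the term"; the two barred terms are IAR and hypersensitivity. The general rule in Protocol 9.4.1.4 is different: "For each AE record only the diagnosis on the AE page of eCRF, do not report the characteristic signs and symptoms of the diagnosis" separately. If there is no diagnosis, that section has each sign and symptom entered until one is available.

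**Identification.** SAP 5.3.1: "The AESI of ISR and hypersensitivity (IAR) will be identified by investigators as captured on case report forms". A sponsor clinical review may add further related events.

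**Counting.** SAP 7.3.2.7.1: "The number of Hypersensitivity (IARs) and number and percentage of patients with Hypersensitivity (IARs) will be presented by treatment cohort and overall", with rows for SOC and PT and a separate listing. SAP 7.3.2.1 gives events and patients for each AE category, with events of special interest as a subcategory. Protocol 11.5.6.2 has IARs handled like any other AE.

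**The concern.** Safety and tolerability are the secondary objective, and IARs are events of special interest in both documents. Readers will compare the three dose cohorts, of about 9 patients each, on these counts.

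A row labelled as a number of IARs will naturally be read as a number of reactions. It will in fact rise with the number of signs each reaction produced and with how finely a site recorded them. The patient count beside it does not supply what is missing: over repeated dosing it cannot separate a patient who reacted once from one who reacted many times. A difference between cohorts in the event count could therefore reflect more reactions, or the same number of reactions with more signs.

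**Working it through.** The plan gives no figure to reproduce. The check sets the recording rule against the counting rule and then follows the arithmetic.

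**1. Unit recorded.** Under Protocol 9.4.2.1.1, a reaction with k recorded signs produces k AE records.

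**2. Unit counted.** Under SAP 5.3.1, 7.3.2.1 and 7.3.2.7.1 and Protocol 11.5.6.2, the AE record is what is counted. Neither document has a rule that joins records from one dose into one reaction, and no planned table counts reactions. The two administrative change letters correct other inconsistencies but not this one.

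**3. Size.** Let a cohort have R reactions, the i-th with s_i recorded signs. The event count is

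E = s_1 + … + s_R = R × (mean signs per reaction),

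so E/R is the mean number of recorded signs per reaction. It is 1 if every IAR has one sign. Illustration, assuming R = 3 and every sign recorded separately:

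| Signs per reaction | Events shown | Reactions |
|---|---|---|
| 1 | 3 × 1 = 3 | 3 |
| 2 | 3 × 2 = 6 | 3 |
| 3 | 3 × 3 = 9 | 3 |
| 4 | 3 × 4 = 12 | 3 |

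The documents give neither a reaction rate nor a distribution of signs per reaction, so the actual factor is unknown.

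**4. Whether the patient count fills the gap.** Each patient is scheduled for 1 single dose plus 3 per week over Weeks 3 to 9, that is 1 + 3 × 7 = 22 doses. Compare two hypothetical cohorts, each with one affected patient:

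| | Events | Patients | Reactions |
|---|---|---|---|
| One reaction with four signs | 4 | 1 | 1 |
| Four single-sign reactions at four doses | 4 | 1 | 4 |

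The totals are identical. If the same sign recurs, the PT row would hint at recurrence (several events, one patient). If the signs differ from dose to dose, the whole table is the same.

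**5. What is not affected.** Single-sign IARs count once. The overall number and percentage of patients with at least one IAR is not inflated, although one patient may appear in several PT rows.

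**The case against.** The strongest reply is that the SAP counts exactly what the protocol defines. Protocol 9.4.2.1.1 describes IARs as signs or symptoms and speaks of AEs characterised as IARs, so the flagged AE is the IAR. A reader might go further and call the SAP count an error against the protocol. The documents do not support that. They do use the term both ways: the same section also refers to a future IAR for which a baseline tryptase value is kept, and to the signs and symptoms of an IAR, which makes it the whole reaction. The defect is an unstated unit and a missing reaction count.

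Other parts of the reply also stand:

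- SAP 7.3 plans no formal safety testing, and patient counts are reported next to event counts.
- A reader might infer that recurrence is hidden altogether. It is not: the IAR listing and the dosing listing with injection date and time (SAP 7.3.1) let reactions be rebuilt by hand. What is lacking is a tabulated count under a pre-specified rule.
- It is tempting to say that each systemic reaction adds between 2 and 5 events. That range rests on an example in the protocol, so neither bound is established.
- It is also tempting to call the two recording rules opposites. Protocol 9.4.2.1.1 reads as a specific exception to 9.4.1.4. However, neither cites the other, and the exception bars only two terms. A site using another diagnostic term could enter one record where a second site enters several. Whether this would happen is unknown, since the completion guidelines and operations manual are not available here.

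**Conclusion.** The point holds in limited form. The planned number of IARs is a count of flagged AE records, so a multi-sign reaction contributes more than one event and no table gives reactions per cohort. The inflation equals the mean number of recorded signs per reaction and cannot be fixed in advance; the 6, 9 and 12 above rest on an assumed three reactions.

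The overall patient incidence is sound, and no hypothesis test depends on the event count. This is a worthwhile, inexpensive improvement to a descriptive safety output: it would separate recurrence over 22 doses from the number of signs per reaction. The conclusion assumes that sites follow the IAR recording rule as written and that no unseen manual defines a reaction-level unit.

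**What to change.** **SAP 7.3.2.7.1 (and the matching line in 7.3.2.1).** Keep the SOC/PT table, but label its event column as IAR-flagged AEs (signs). Add, by cohort and overall:

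- number of reactions, where one reaction is all IAR-flagged AEs in one patient linked to the same dose by dose time and AE onset;
- number and percentage of patients with at least one reaction;
- number and percentage of patients with repeat reactions.

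Link to the dose rather than the injection, because Protocol 8.1 allows several injections per dose.

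**Assignment rules.** State how AEs with missing onset time, and sponsor-identified events outside the 3-hour window (SAP 5.3.1 states no time limit for these), are handled. For example, assign them to the most recent preceding dose and flag them. Where no usable onset date exists, show the AE as unassigned.

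**Protocol 9.4.1.4.** Add a cross-reference naming the IAR rule in 9.4.2.1.1 as its exception, so that all sites record the same unit.

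**Cost.** SAP wording, one protocol clarification and a small derivation from dose and AE times already collected. The downside is that some reactions will be assigned by rule when onset times are incomplete, which is why the flag is needed.

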#### 7.3.2.7.2. Adverse Events of Special Interest: Ectopic Calcification

All observed MedDRA PTs identified in the Alexion clinical review to be ectopic calcification AESIs will be presented alphabetically in a data listing.

The number of ectopic calcification AESIs, TEAEs within this AESI category, and the number and percentage of patients with events will be presented by treatment cohort and overall by SOC and PT.

#### 7.3.2.7.3. Adverse Events of Special Interest: Lipodystrophy

Events of lipodystrophy will be analyzed using the same approach described above for events of ectopic calcification.

#### 7.3.2.7.4. Adverse Events of Special Interest: Craniosynostosis

Events of craniosynostosis will be analyzed using the same approach described above for events of ectopic calcification.

#### 7.3.2.7.5. Adverse Events of Special Interest: Chronic Hepatitis

Events of chronic hepatitis will be analyzed using the same approach described above for events of ectopic calcification.

#### 7.3.3. Other Safety

#### 7.3.3.1. Analyses for Laboratory Tests

Actual values and changes from treatment baseline will be summarized descriptively for patients with available data for each laboratory parameter by treatment cohort and overall. Missing laboratory data will not be imputed and only scheduled assessments will be summarized in table summaries; any unscheduled assessments will be included in by-patient data listings and will be flagged as such. A summary for "Last Assessment" will be included for the last available post-treatment baseline result for each patient. See Appendix 9.3 for the definition of Treatment Baseline for Safety analyses, and refer to Table 4 on how to handle the PTH values fall under the LLOQ.

All laboratory values will be classified as normal, below normal (low), or above normal (high) based on normal ranges supplied by the central laboratory and shift tables will be produced showing the shift from treatment baseline to post-treatment baseline assessments. Frequencies of abnormal values will be presented in tabular form. A summary of shifts to Last Assessment will also be included.

For selected laboratory assessments, for example, ALP, figures over time may be produced. For purposes of analyses, laboratory results based upon standardized units will be used.

A listing of all laboratory data will be presented by treatment cohort, patient identification, visit, and laboratory parameter.

#### 7.3.3.2. Vital Signs

Actual values and changes from treatment baseline in vital signs (blood pressure, heart rate, respiratory rate, temperature) at each visit will be summarized descriptively for patients with available data by treatment cohort and overall. Missing vital signs data will not be imputed and only scheduled assessments will be summarized in tables; unscheduled assessments will be presented in by-patient data listings and flagged as such. A summary for "Last Assessment" will be included for the last available post-treatment baseline result for each patient.

A listing of all vital signs data will be presented by treatment cohort, patient identification, and visit with each vital sign result for the visit listed in the same row. A separate listing of patient weight data at each visit will also be presented with unit standardized to kg.

#### 7.3.3.3. Physical Examination

Physical examination findings will be summarized descriptively by treatment cohort and overall for each timepoint using counts and percentages. A summary for "Last Assessment" will be included for the last available post-treatment baseline result for each patient. A listing of all physical examination data will be presented by treatment cohort, patient identification, visit, and body system.

#### 7.3.3.4. Renal Ultrasound

The following renal ultrasound findings will be summarized by treatment cohort and overall for each timepoint using counts and percentages:

-Nephrocalcinosis (yes/no)

-Normal/Abnormal Not Clinically Significant not related to underlying condition/Abnormal Not Clinically Significant related to underlying condition/Abnormal Clinically Significant

Listings of all renal ultrasound results will be provided by treatment cohort, patient identification, and visit, including any free text response for 'Findings'.

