#### Safety:

The incidence of treatment-emergent adverse events (TEAEs) and serious adverse events (SAEs) will be summarized by System Organ Class (SOC) and Preferred Term (PT) overall, by severity, and by relationship to study drug. Changes from Baseline in vital signs, laboratory assessments (chemistry, hematology, and urinalysis) will be summarized. Shifts from Baseline in laboratory assessments as well as physical examination, renal ultrasound, and ophthalmology findings will be summarized for all study visits. Immunogenicity data will be tabulated and summarized.

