## 11.5.6.6. Safety Variables: Vital Signs, Physical Examinations, Renal Ultrasounds, and Ophthalmology Assessments

Actual values and changes from Baseline in vital signs (blood pressure, heart rate, respiratory rate, and temperature) will be summarized by cohort and timepoint using descriptive statistics. Physical examination (including weight), renal ultrasound, and ophthalmology findings will be summarized by cohort and timepoint using counts and percentages. Listings of abnormal results will be provided.

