#### 5.3.6. Ophthalmology Assessment

A full ophthalmology examination will be performed at the times specified in Appendix 9.1. The examination will assess for papilledema and signs of ectopic calcification, and will include assessments of visual acuity; adnexa; and slit-lamp biomicroscopy with examination of anterior chamber, lens, conjunctiva, cornea, fundus, and other.

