#### 7.3.3.5. Ophthalmology Assessment

The following ophthalmology examination findings will be summarized by treatment cohort and overall for each timepoint and eye (left and right), using counts and percentages:

Normal/Abnormal Not Clinically Significant not related to underlying condition/Abnormal Not Clinically Significant related to underlying condition/Abnormal Clinically Significant for the following:

- Adnexa, Eye Movements, Intraocular Pressure
- Visual Acuity
- Slit-lamp Biomicroscopy categories: Anterior Chamber, Lens, Conjunctiva, Cornea, Fundus, Other

Is Visual Acuity impacted by any abnormality observed' (yes/no)

Listings of all ophthalmology assessments will be provided by treatment cohort, patient identification, and visit, including any free text response for 'Findings' where calcifications should be noted.

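### Renal ultrasound, eye and physical examination findings are tabulated only as counts per timepoint, although the synopsis reads as promising shifts from Baseline, so the planned tables alone generally do not give the number of new findings

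*SAP*

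**What the plan says.** The protocol describes these summaries in two places, and they differ.

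- **Protocol synopsis, Statistical methods, Safety:** "Shifts from Baseline in laboratory assessments as well as physical examination, renal ultrasound, and ophthalmology findings will be summarized for all study visits".
- **Protocol Section 11.5.6.6:** "renal ultrasound, and ophthalmology findings will be summarized by cohort and timepoint using counts and percentages", together with listings of abnormal results. It mentions no shift.

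The SAP follows the second.

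- **SAP 7.3.3.4 (renal ultrasound):** "The following renal ultrasound findings will be summarized by treatment cohort and overall for each timepoint using counts and percentages". The items are nephrocalcinosis (yes/no) and a four-level overall result.
- **SAP 7.3.3.5 (eye):** "The following ophthalmology examination findings will be summarized by treatment cohort and overall for each timepoint and eye (left and right), using counts and percentages". The items are individual eye structures and functions, graded on the same four levels, plus one question on visual acuity. Calcification belongs to the free-text findings in the listing, "where calcifications should be noted".
- **SAP 7.3.3.3 (physical examination):** counts per timepoint plus a summary of the last assessment, again without a shift.

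SAP 5.3.6 states the aim of the eye examination: "The examination will assess for papilledema and signs of ectopic calcification". SAP 4.1, which lists changes from the protocol's analyses, says nothing about these summaries.

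**The concern.** Table 2 of the protocol schedules renal ultrasound and the eye examination once in the Run-in Period and once at Week 13/EOS. With one examination before treatment and one after, most of what they can say about safety lies in the change within each patient. A table of counts at each visit does not show that change.

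SAP 5.3.1 names ectopic calcification an adverse event of special interest, and safety is the study's secondary objective. A reader of the report will want to know how many patients in each dose cohort developed nephrocalcinosis or ocular calcification on treatment, out of those free of it at the start. No planned table answers that directly. For the eye, no table isolates calcification or papilledema even at a single visit.

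The treatment of other safety data makes the gap stand out. The SAP plans shift tables for laboratory values (7.3.3.1), changes from baseline for vital signs (7.3.3.2) and baseline-to-post-baseline shifts for antibody status (7.3.3.7).

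**Working it through.** The plan gives no figure to reproduce here. The check is what two separate counts can say about new cases.

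**Inputs.** Cohort size is 9, 27 in total (SAP 9.2). There are two scheduled examinations per patient (Protocol Table 2). The documents give no Baseline prevalence of nephrocalcinosis or ocular calcification, so the counts below are assumptions for illustration.

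**Formula.** Take N patients with both examinations, b positive at Run-in and e positive at Week 13. Let r be the number whose finding resolves and k the number with a new finding. Then

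e = b − r + k, so k = e − b + r.

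The table shows b and e but not r. New cases can come only from the N − b patients who were negative at Run-in, and cannot exceed e. Hence

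max(0, e − b) ≤ k ≤ min(e, N − b).

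**Results for N = 9.**

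| Run-in | Week 13 | New cases possible | New cases if nothing resolves |
|---|---|---|---|
| 0/9 | 2/9 | exactly 2 | 2 |
| 1/9 | 1/9 | 0 to 1 | 0 |
| 2/9 | 4/9 | 2 to 4 | 2 |
| 3/9 | 3/9 | 0 to 3 | 0 |
| 4/9 | 3/9 | 0 to 3 | not applicable: at least one resolved |

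In the 3/9 and 3/9 row the range is 0% to 33% of the cohort (3/9), or 0% to 50% of the patients free of the finding at Run-in (3/6). The upper end needs three findings to resolve while three others appear.

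**When the counts suffice.** The bounds coincide if b = 0, b = N, e = 0 or e = N. They also settle the matter if findings never resolve, since r = 0 gives k = e − b. Otherwise the table leaves a range. All of this assumes both examinations are available for every patient counted.

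**What the AE tables add.** Protocol 9.3.4 and 9.3.5 require clinically significant changes from Baseline to be recorded as AEs. SAP 5.3.1 and 7.3.2.7.2 then identify and tabulate ectopic calcification events. That leaves new findings judged not clinically significant and not otherwise reported as AEs. They enter the Week 13 count but are counted as new in no table.

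**Eye targets.** SAP 7.3.3.5 grades ten items per eye: adnexa, eye movements, intraocular pressure, visual acuity and six slit-lamp categories including fundus. An affected structure can therefore register as abnormal, but the table does not say whether the reason is calcification, papilledema or something else.

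**The case against.** The strongest reply is that nothing is lost. SAP 7.3.3.4 and 7.3.3.5 list every renal and eye result by patient and visit with the free text, and SAP 7.3 promises by-patient listings of all safety data. With 27 patients and two examinations each, pairing by hand is feasible. This stands. A reader might infer that new calcification cannot be distinguished from old at all, and the documents do not support that. The limitation is in the tables. A listing still gives no prespecified numerator and denominator by cohort.

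A reader might also infer that the SAP departed from the protocol. It did not depart from Section 11.5.6.6, which it follows. The conflict lies between the synopsis and the body of the protocol. The synopsis sentence can even be parsed so that shifts apply to laboratory values only, which would match the body. That parse is strained, but it is a reason to reconcile the text rather than to allege a breach.

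Nor do the documents say that only clinically significant changes can become AEs. Protocol 9.3.4 and 9.3.5 say such changes must be recorded. Section 9.4.1 defines an AE broadly, and 9.4.1.2 adds triggers such as a need for further diagnostic testing. The residual gap is therefore narrower than a blanket exclusion of other findings.

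Finally, the 3/9 and 3/9 example is a bound and not a forecast. Nothing in the documents suggests that three findings would resolve over the study. The result codes allow for abnormalities related to the underlying condition, but that is not evidence of how common they are at Run-in.

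**Conclusion.** The point holds as a gap in tabulation and an unreconciled inconsistency. On its natural reading the synopsis calls for shifts from Baseline in renal ultrasound, ophthalmology and physical examination findings. The protocol body and the SAP provide counts per timepoint, and SAP 4.1 is silent.

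The size depends on Run-in prevalence and on whether findings resolve, neither of which the documents give. If no patient is positive at Run-in, or no finding resolves and all examinations are available, the planned counts yield the number of new cases. Otherwise they yield a range, which in a cohort of 9 can span a few patients. New findings judged not clinically significant and not reported as AEs are visible as new only by pairing listings. Ocular calcification and papilledema have no yes/no item of their own.

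The primary endpoint is unaffected. This is a worthwhile, inexpensive improvement to the safety reporting on a named event of special interest, using data already collected.

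**What to change.** 1. Reconcile the synopsis with Protocol Section 11.5.6.6, so that both say the same about renal ultrasound, ophthalmology and physical examination. Where shifts are not going to be produced, declare that in SAP 4.1.
2. In SAP 7.3.3.4, add a within-patient shift table from Run-in to Week 13/EOS for nephrocalcinosis (yes/no) and another for the overall result category. Report the incidence of new nephrocalcinosis among patients free of it at Run-in, by cohort.
3. In SAP 7.3.3.5, code ocular calcification (yes/no) and papilledema (yes/no) from the findings text before database lock, under a written rule. Give one patient-level shift table for each. A shift table for every eye item is not needed: ten items in two eyes would make 20 sparse tables.

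The cost is four extra tables, sparse at about 9 patients per cohort, and coding the free text of about 54 scheduled eye examinations (27 patients × 2 visits). One examination may carry more than one text entry, so the number of entries could be higher. No new assessments are required.
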